#### 1.2. Risk/Benefit Assessment

Current treatments for IIH have limited efficacy and can cause disabling side effects. Acetazolamide, the most commonly used drug (off licence) has a high side effect profile (48% discontinued in a clinical trial due to intolerable side effects) [Ball, 2011]. Although IIH is a rare condition, incidence is rising with rising obesity trends. Improving IIH morbidity with new therapeutics is clearly an unmet need.

Safety data for Presendin (exenatide) is based on the IB (Pepton Inc.). Warnings include pancreatitis, hypoglycaemia when used in combination with a sulfonylurea, renal impairment, severe gastrointestinal disease and hypersensitivity.

Invex Therapeutics has considered these warnings and has defined eligibility criteria to ensure patient safety is paramount. As such patients with known contraindications to GLP-1 agonists, such as pancreatitis, ketoacidosis, severe gastrointestinal disease and renal impairment, will not be included. Additionally, diabetic patients receiving glucose lowering medication will be excluded.

An Independent Adjudication Committee (IAC), as described in Section 14.5, will assist the Investigators (when required) with the eligibility criteria of the patients to be enrolled,

Study Number: INVEX-CLIN-IIH-301	Compound No.: Presendin
Protocol	Version: 3.0

and also to determine treatment failures to ensure patient safety and the efficacy of the trial.

The most common adverse reactions experienced with exenatide are nausea, hypoglycaemia (only when used with other glucose lowering drugs, but these patients are excluded from the trial), vomiting, diarrhoea, feeling jittery, dizziness, headache and dyspepsia.

Patients receiving the active treatment during the randomised period may benefit by experiencing an improvement in their IIH symptoms, although this cannot be guaranteed.

## **2. OBJECTIVES**

### **2.1. Primary Objective**

To determine the efficacy of Presendin administered subcutaneously once weekly for 24 weeks to patients with IIH, as determined by change in ICP, as measured by LP at baseline and at 24 weeks.

The baseline LP is the diagnostic LP.

### **2.2. Secondary Objectives**

To determine the effect of Presendin on change in:

- Perimetric Mean Deviation as measured by Humphrey Visual Field analysis (24-2 SITA-Standard)
- Papilloedema by change in optical coherence tomography (retinal nerve fibre layer (RNFL) thickness and optic nerve head size)
- Monthly headache days (MHD)
- Moderate to severe monthly headache days
- Headache responder rate ( $\geq 50\%$  reduction in monthly headache days)
- Headache responder rate ( $\geq 50\%$  reduction in moderate to severe monthly headache days)
- Headache severity
- Monthly use of acute headache analgesic medications
- Visual acuity
- Treatment failure

Study Number: INVEX-CLIN-IIH-301 Protocol	Compound No.: Presendin Version: 3.0
---	--

### **2.3. Safety Objective**

To determine the safety of Presendin administered subcutaneously once weekly as determined by vital signs, the occurrence of adverse events (AEs), electrocardiogram (ECG) and routine laboratory assessments.

### **2.4. Exploratory Objectives**

To determine the effect of Presendin on:

- Macular ganglion cell layer/complex thickness
- Headache responder rate:  $\geq 30\%$  reduction in monthly headache days
- Headache responder rate:  $\geq 30\%$  reduction in moderate to severe monthly headache days
- Patient Reported Outcomes
- Body Mass Index
- Body Weight
- Health Utilisation

## **3. ENDPOINTS**

### **3.1. Primary Endpoint**

The primary endpoint is the change in ICP from baseline to Week 24 measured by LP.

The baseline LP is the diagnostic LP.

### **3.2. Secondary Endpoints**

- Perimetric Mean Deviation
- Retinal nerve fibre layer (RNFL) thickness
- Optic nerve head size
- The number of monthly headache days (MHD). Monthly headache days will include all headache days, defined as those with an onset, continuation or recurrence, any severity or phenotype of headache, lasting at least 30 minutes or which require acute headache analgesia.

Study Number: INVEX-CLIN-IIH-301	Compound No.: Presendin
Protocol	Version: 3.0

- Number of monthly moderate to severe headache days. A moderate/severe headache day will be defined as a day with moderate or severe pain that lasts at least 4 hours or that requires acute headache analgesic medications
- Responder rate monthly headache days (defined as a  $\geq 50\%$  reduction)
- Responder rate moderate to severe monthly headache days (defined as a  $\geq 50\%$  reduction)
- Headache severity (assessed by 11-point Numeric Rating Scale [NRS], 0-10 where 0 = no pain and 10 = most severe pain)
- Use of acute headache analgesic medications (acute headache analgesics in days per month)
- Visual acuity, as measured by logarithm of the minimum angle or resolution (LogMAR) units
- Treatment failure, defined as initiation of either medical therapy or a surgical intervention to lower ICP.\*

\*criteria defined in rescue therapy section [10.1.1](#)

### 3.3. Safety Endpoints

- Vital Signs
- Adverse events: Treatment-emergent adverse events (TEAEs), , serious adverse events (SAEs)
- Resting 12-lead electrocardiogram
- Routine laboratory assessments (haematology, biochemistry and urinalysis)

### 3.4. Exploratory Endpoints

- Macular ganglion cell layer/complex thickness
- Responder rate monthly headache days (defined as  $\geq 30\%$ )
- Responder rate moderate to severe monthly headache days (defined as  $\geq 30\%$  reduction)
- Patient Reported Outcomes (PRO):
  - Visual Function Questionnaire-25 and 10-item supplement
  - Headache Impact Test-6
  - 36-item short form survey

Study Number: INVEX-CLIN-IIH-301	Compound No.: Presendin
Protocol	Version: 3.0

- EuroQol -5 dimension -5 level survey
- Patient Global Impression of Change
- Body Mass Index
- Body Weight
- Health Utilisation

## **4. TRIAL DESIGN**

### **4.1. Summary of Trial Design**

#### **4.1.1. Trial Design**

This will be a randomised, placebo-controlled, double-blind, multi-centre clinical trial in approximately 240 randomised patients with IHH.

The trial will begin with a 1-week screening period. Although a headache diary is typically over 28 days, it was felt unethical to have patients off treatment for this more prolonged period. Headache diaries designed to measure headache frequency have been successfully utilised over shorter time periods in previous IHH trials and noted to be representative [NORDIC, 2018; Mollan, 2021b]. Hence the baseline headache frequency will be calculated over 1 week. Patients will be provided with training on the self-administration of the trial medication from the site trial coordinator and provided with a leaflet to take home at the screening visit. Patients will be asked to self-administer placebo during the screening visit to ensure they are comfortable with self-injection. Patients who are not comfortable with self-administration will be deemed screen failures, and not be randomised into the trial. The purpose of the screening period will be to establish baseline measurements and assess trial eligibility.

The screening period will be followed by a 24-week randomised double-blind treatment period in which patients will be randomised (1:1) to receive a SC dose of either Presendin (containing 2mg of exenatide (active group) or matching placebo (placebo group), self-administered once weekly.

At the end of the randomised treatment period (week 24), all patients will have an end of treatment clinic visit. Five weeks after the end of that treatment visit, an end of trial safety follow-up telephone visit will be performed. In the event of any abnormal safety assessments or ongoing adverse event(s) identified at end of treatment; for example, an abnormal ECG or abnormal routine laboratory results, this visit may be performed at the clinic and a safety follow-up performed as appropriate.

Study Number: INVEX-CLIN-IIH-301	Compound No.: Presendin
Protocol	Version: 3.0

[figure not shown]
The duration of the randomised treatment period was felt to be appropriate as the previous phase 2 trials of Exenatide in IIH demonstrated efficacy by 3 months. Additionally, an alternative off label drug used in IIH (acetazolamide) was evaluated over a 6-month period. Hence efficacy is relevant over this time frame. A longer period of randomisation would not be ethical if patients were expected to remain on placebo for 12 months as this could place their overall health at risk.

Assessments will be performed as outlined in [Table 1](#).

A schematic diagram of the trial can be seen in [Figure 1](#).

Study Number: INVEX-CLIN-IIH-301 Protocol	Compound No.: Presendin Version: 3.0
---	--

**Figure 1: Schematic Diagram**

#### 4.1.2. Randomisation and Blinding

At the end of the Screening period, eligible patients will be randomised to receive either Presendin or matching placebo in a 1:1 ratio using a computer system to generate randomisation codes.

Investigators and other site personnel, patients, contract research organisation and Sponsor personnel will be blinded regarding the treatment during the randomised period. Only designated unblinded staff, not involved in the operational conduct of the trial, will be aware of the randomisation codes.

The placebo will have the same appearance and reveal no differences, during administration, to either the Investigator or the patient.

#### 4.1.3. Duration of Patient Participation

The duration of the trial for each patient will be up to 30 weeks, which includes a 1-week screening period, a 24-week randomised treatment period and a treatment follow-up period of 5 weeks.

### 4.2. Stopping Rules

#### 4.2.1. Trial Stopping Rules

There are no trial-specific stopping rules. The Sponsor maintains the right to stop the trial at any point. If this is done, then the Sponsor will provide the Investigators with the rationale for such early termination.

Study Number: INVEX-CLIN-IIH-301	Compound No.: Presendin
Protocol	Version: 3.0

#### **4.2.2. Individual Stopping Rules**

Patients will be withdrawn from the trial medication if they are unable to tolerate the trial medication and will continue to attend trial visits as per protocol. See Section 11 for further details. A Data Safety Monitoring Committee (DSMC) will be involved in decisions for patient safety (Section 14.6).

#### **4.3. End of Trial**

The end of trial is defined as last patient last visit.

### **5. TRIAL POPULATION**

#### **5.1. Number of Patients**

It is anticipated that approximately 350 patients will be required to enter the screening phase for 240 patients to be randomised into the treatment phase.

#### **5.2. Eligibility Criteria**

##### **5.2.1. Inclusion Criteria**

Patients must not be enrolled unless they meet all the following criteria:

1. Age  $\geq 18$  years at the time of consent
2. Diagnosis of new IHH by consensus criteria (see Section 16.1, Appendix 1), including normal structural brain imaging (excluding features of raised intracranial pressure and incidentalomas), including either magnetic resonance venography or computed tomographic venography to exclude thrombosis and no evidence of a secondary causes of raised intracranial pressure
3. Newly diagnosed patients with screening commenced no more than 4 weeks after the diagnostic LP
4. Lumbar puncture opening pressure  $\geq 25$  cm cerebrospinal fluid (CSF) at diagnosis
5. Presence of bilateral papilloedema (Frisén grade  $\geq 1$ ). Verification of papilloedema by the OCT Reading Centre. Where there is uncertainty fundus photography and/or ultrasound scan (B scan) of the optic nerves should be conducted for evaluation by the Independent Adjudication Committee (IAC)
6. Perimetric Mean Deviation (PMD) defined as between -2 to -7 decibels (dB) in at least one eye. Eyes meeting this criteria will be defined as ‘study eyes’

Study Number: INVEX-CLIN-IIH-301 Protocol	Compound No.: Presendin
	Version: 3.0

7. Reproducible visual loss present on automated perimetry including no more than 15% false positive responses, (reliability confirmed by the Visual Field Reading Centre) in study eyes
8. Two or more headache days over the 7-day period prior to screening and also the patient must meet this criterion during the 7-day screening period
9. Females of childbearing potential must have a negative pregnancy test and must agree to use a highly effective birth control method (failure rate less than 1% per year when used consistently and correctly – see Section 16.7, Appendix 7 for further details) during the whole trial duration including the last follow-up visit (12 weeks after ceasing drug). Female patients who are lactating must agree to stop breast-feeding. Or female patients of non-childbearing potential (defined as pre-menopausal females with a documented tubal ligation or hysterectomy; or post-menopausal females defined as 12 months of amenorrhoea [in questionable cases a blood sample with simultaneous follicle stimulation hormone (FSH) 25-140 IE/L and oestradiol <200 pmol/L is confirmatory])
10. Male patients with a female partner of childbearing potential must commit to practice methods of contraception (e.g., condom, vasectomy) and abstain from sperm donation during the trial including the last follow-up visit (12 weeks after ceasing drug). Their partners, if they are women of childbearing potential, must agree to practice contraception and to use a highly effective method of contraception during the trial, including the last follow-up visit (12 weeks after ceasing drug)
11. Able to provide written informed consent

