In the 4 weeks prior to visit 10, patients must not have missed more than one dose of trial medication and must have self-administered their final dose within 7 days of visit 10. Patients will be reminded by the trial site to self-administer trial medication weekly, to continue this until the completion of visit 10 and to bring their trial medication with them at visit 10 for return.

Where more than one dose has been missed during the 4 weeks preceding visit 10, visit 10 should be delayed. Self-administration of trial medication should continue at 7-day intervals and then visit 10 rescheduled to ensure no more than one dose of the trial medication has been missed in the previous 4 weeks. Visit 10 should be delayed no more than 14 days.

- Concomitant medication review
- Headache preventative medication review
- Headache diary review

Study Number: INVEX-CLIN-IIH-301 Protocol	Compound No.: Presendin
	Version: 3.0

- Vital signs (triplicate readings for blood pressure and heart rate will be taken at 1-minute intervals)
- Body weight and BMI
- Adverse event review
- Targeted physical examination
- Urine pregnancy test for women of child-bearing potential
- Electrocardiogram
- Visual Assessments to both eyes
  - Optical coherence tomography Imaging
    - Sites should initially check the scan quality. The OCT scan should then go through the upload process to the OCT Reading Centre, without delay. The OCT scan will then be reviewed by the OCT Reading Centre for a full quality assessment. The report from the OCT Reading Centre will be sent to the site. Where the OCT is of insufficient quality it should be repeated as soon as possible at an unscheduled visit. Where the OCT processing is of insufficient quality it should be reprocessed as soon as possible by the site.
  - Humphrey Visual Field (24-2 SITA-Standard)
    - Sites should initially check the performance quality of the HVF (to ensure no more than 15% false positives). The HVF should then be uploaded to the Visual Field Reading Centre without delay (an initial quality assessment takes place during the upload procedure). The HVF will then be reviewed by the Visual Field Reading Centre for a full quality assessment. The report from the Visual Field Reading Centre will be received by the site. Where the visual field is of insufficient quality it should be repeated at an unscheduled visit without delay.
  - Visual Acuity (LogMAR score)
- Lumbar puncture (within 7 days of last dose of trial medication)

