#### **6.1.6. Visit 11 Follow-Up**

This visit will be performed as a telephone call to conduct headache preventative medication review and check for any AEs or changes in medication. In the event of any abnormal safety assessments identified at the end of treatment, e.g., abnormal ECG, abnormal routine laboratory results or ongoing adverse events, this visit may be performed at the clinic to repeat or follow up safety assessments.

A urine pregnancy test (for women of childbearing potential) will be performed, this can be conducted at home if the visit is performed by telephone call.

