#### **6.2.2.4.5. Pregnancy**

At screening blood will be collected to enable a serum pregnancy test to be performed. At visits thereafter, urine will be collected from female patients of childbearing potential at the times outlined in the Time and Events table ([Table 1](#)) to enable highly sensitive urine-based pregnancy tests to be performed. Female patients who are identified as being pregnant during the trial will be withdrawn from further treatment but will continue to attend safety follow-up visits.

The Investigator or designee should report any pregnancies in female patients to the Sponsor or designee, using the Pregnancy Report Form, within 24 hours. The contact details for reporting are:

[REDACTED]

Female patients or partners of patients who become pregnant should be followed until delivery, stillbirth or termination. The outcome of the pregnancy and, if applicable, the health of the baby, should be reported to the Sponsor using the Pregnancy Report Form.

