### **12.3. Reporting and Handling of Pregnancies**

Pregnant patients will be withdrawn from the trial.

Female patients will be instructed to notify the Investigator immediately if they become pregnant during the trial and up to 12 weeks after discontinuation/completion of trial medication. Pregnant patients will be withdrawn from further trial treatment. The patients will also be instructed to report pregnancies discovered after the last visit, if they believe that conception occurred during their participation in the trial.

A pregnancy as such is not an AE, unless there is a possibility that the trial medication has interfered with the efficiency of any contraceptive measures. The Investigator should report all pregnancies to the Sponsor contact or designee within 24 hours of being informed of them. The pregnancy report form should be used instead of the SAE form.

The pregnant patients will be followed until the end of the pregnancy. Any complication during the pregnancy should preferably be reported as an AE. The outcome of the pregnancy must be reported on the pregnancy report form. Any spontaneous abortion, stillbirth, birth defect/congenital anomaly, death, or other serious infant condition must be reported and followed up as an SAE.

Patients will give consent on enrolment that the Investigator will report any pregnancy to the Sponsor and that further information will be collected until delivery.

Study Number: INVEX-CLIN-IIH-301 Protocol	Compound No.: Presendin
	Version: 3.0

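### Version 3.0 ends contraception at a last follow-up visit it dates 12 weeks after stopping drug, but that visit falls about 4 to 7 weeks after the last dose for patients who complete treatment

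*Protocol*

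**What the plan says.** The point concerns protocol Version 3.0, the latest version whose eligibility criteria are available.

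- **Contraception, women (Section 5.2.1, criterion 9; also the Protocol Summary):** required "during the whole trial duration including the last follow-up visit (12 weeks after ceasing drug").
- **Contraception, men and their partners (criterion 10; also the Protocol Summary):** male patients must use contraception and "abstain from sperm donation during the trial including the last follow-up visit (12 weeks after ceasing drug"). Their partners of childbearing potential are held to the same end point.
- **Timing of the follow-up visit (Section 4.1.1):** "Five weeks after the end of that treatment visit, an end of trial safety follow-up telephone visit will be performed". Section 4.1.3 makes up the participation time from a 1-week screening period, "a 24-week randomised treatment period and a treatment follow-up period of 5 weeks". Table 1 puts Visit 10 at Day 169 (Week 24) and Visit 11 at Day 204 (Week 29).
- **Last dose (Section 6.1.5):** patients "must have self-administered their final dose within 7 days of visit 10".
- **Last pregnancy test (Section 6.1.6, Visit 11):** "A urine pregnancy test (for women of childbearing potential) will be performed, this can be conducted at home".
- **Pregnancy notification (Section 12.3):** "Female patients will be instructed to notify the Investigator immediately if they become pregnant during the trial and up to 12 weeks" after trial medication ends. No visit is named.
- **Partner pregnancies (Section 6.2.2.4.5):** "Female patients or partners of patients who become pregnant should be followed until delivery, stillbirth or termination".

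**The concern.** Criteria 9 and 10 give one obligation two end dates. The words name a visit; the bracket gives a time. For a patient who completes treatment the two do not coincide, and no visit in the schedule falls 12 weeks after the last dose.

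This is a binding participant-safety rule, in a disease the protocol describes as most frequent in obese women of childbearing age, so it will apply to much of the sample. Staff who look up the last follow-up visit in Table 1 find Visit 11. The final pregnancy test is done there, and adverse event reporting stops there (Table 1, footnote 15). Treating it as the end of the contraception requirement is a natural reading. After Week 29 a pregnancy is detected only if the patient reports it under Section 12.3.

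A related gap lies in Section 12.3. Its 12-week notification instruction is addressed to female patients only, although criterion 10 binds male patients and their partners and Section 6.2.2.4.5 expects partner pregnancies to be followed to outcome.

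**Working it through.** **Inputs (Version 3.0)**

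| Item | Value | Source |
|---|---|---|
| Visit 10 | Day 169 | Table 1 |
| Visit 11 | Day 204, window ±5 days | Table 1 |
| Anchor of Visit 11 | 5 weeks after the end-of-treatment visit | Section 4.1.1 |
| Last dose | 0 to 7 days before Visit 10 | Section 6.1.5 |
| Contraception limit | 12 weeks × 7 = 84 days after ceasing drug | Section 5.2.1, criteria 9 and 10 |

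**The plan's own figures.** Visit 11 minus Visit 10 = 204 − 169 = 35 days = 5.0 weeks. Total participation = 1 + 24 + 5 = 30 weeks. Both agree with Section 4.1.3, so the schedule is consistent with itself. The bracket in the criteria is what does not fit it.

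**Last dose to Visit 11, for a patient who completes treatment.** Interval = 35 days + (Visit 11 window) + (days from last dose to Visit 10).

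- Shortest: 35 − 5 + 0 = 30 days (4.3 weeks)
- Longest: 35 + 5 + 7 = 47 days (6.7 weeks)
- Visit 11 on its nominal date: 35 to 42 days

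**Shortfall against 12 weeks.** Shortfall = 84 − interval.

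- Smallest: 84 − 47 = 37 days (5.3 weeks)
- Largest: 84 − 30 = 54 days (7.7 weeks)
- Nominal: 84 − 42 = 42 days to 84 − 35 = 49 days. As study days, a last dose on Day 162 to 169 puts the 12-week point at Day 246 to 253, against Visit 11 on Day 204.

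**Sensitivity to the anchor.** If Visit 10 (±14 days) and Visit 11 (±5 days) were both counted from Day 1, the interval would run from 199 − 183 = 16 days to 209 − (155 − 7) = 61 days. The shortfall would then be 84 − 61 = 23 days to 84 − 16 = 68 days (3.3 to 9.7 weeks). Section 4.1.1 anchors Visit 11 to the end-of-treatment visit, so the narrower range is used.

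**Patients who stop drug early.** Someone who stops but stays in follow-up reaches Visit 11 at least 12 weeks after the last dose if that dose was on or before Day 204 − 84 = Day 120 (Week 17). For them there is no shortfall.

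**Which half is wrong.** Twelve weeks is the only duration in the sentence, and Section 12.3 uses the same limit independently of any visit. The visit label is therefore the faulty part. Version 1.0 carried the same phrase when Visit 11 was at Day 197, which is 197 − 169 = 28 days after Visit 10. Version 3.0 moved the visit and added a pregnancy test there, but left the phrase as it was.

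**The case against.** The strongest reply is that the right number is printed beside the wrong label. A reader who applies the stated 12 weeks gets the intended rule, Section 12.3 supports it, and no section tells sites to release patients from contraception at Visit 11. That is true and limits the harm. It does not remove the ambiguity: the governing words tie the obligation to the trial's duration and a named visit, and the schedule gives that visit a different date.

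Second, Version 3.0 is not the latest version. Appendix pages of Version 4.0 are present, but its eligibility criteria, schedule and Section 12.3 are not. The phrase may already have been corrected. It survived from Version 1.0 to Version 3.0, so correction cannot be assumed; the recommendation is made conditional.

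Third, reliance on self-report after Week 29 is a deliberate provision of Section 12.3 and no defect in itself. This stands, and further contact is suggested only as an option.

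Fourth, partner pregnancies are partly covered, since Section 6.2.2.4.5 requires follow-up and Section 12.3 has the investigator report all pregnancies. What is missing is narrow: an instruction that tells male patients to notify. The main correction does not depend on it.

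Fifth, Section 6.1.5 lets the lumbar puncture be re-booked or Visit 10 be split, with dosing continued. If Visit 11 were timed from the first Visit 10 date, it could fall fewer than 30 days after the last dose. That would only widen the shortfall.

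**Conclusion.** The contradiction holds in Version 3.0. For patients who complete treatment, the visit named in criteria 9 and 10 comes 37 to 54 days before the 12-week point stated in the same phrase. The range assumes that Visit 11 is timed from the actual Visit 10, within its ±5-day window, and that the last dose is 0 to 7 days before Visit 10. It does not apply to patients who stop drug by about Day 120 and remain in follow-up.

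No claim is made about drug levels or foetal risk between Visit 11 and 12 weeks, because the protocol gives no elimination time after the last dose. Sample size, power and the primary analysis are unaffected. It should still be corrected, because it is a safety obligation with two end dates.

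**What to change.** Check Version 4.0 first. If the phrase is still there:

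1. In criteria 9 and 10 (Section 5.2.1) and in the Protocol Summary, replace it with: *during the trial and until 12 weeks after the last dose of trial medication*. Remove the equation with the last follow-up visit.
2. Use the same wording in the consent form.
3. In Section 12.3, extend the 12-week notification instruction to pregnancies in partners of male patients.
4. Optionally, add a telephone contact or home pregnancy test after Week 29.

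The cost is one phrase in the two criteria and the summary, one sentence in Section 12.3, and matching consent wording. No added visit is required.
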